#### **8.1.4 Long-term Follow-up**

Long-term follow-up phone call at 6 months ( $\pm 1$  week) after last dose of protocol required therapies to collect information on serious adverse events, survival, start of new therapies, and disease status.

#### **8.1.5 End of Study**

The end of study will be the day of the last scheduled long-term follow-up call.

### **8.2 Description of General Study Assessments and Procedures**

The sections below provide a description of the individual study procedures for required time points.

**8.2.1 General Assessments****8.2.1.1 Informed Consent**

All subjects or their legally authorized representative must sign and personally date the IRB/IEC approved informed consent before any study-specific procedures are performed.

**8.2.1.2 Demographics**

Demographic data collection including sex, age, race, and ethnicity will be collected in order to study their possible association with subject safety and treatment effectiveness. Additionally, demographic data will be used to study the impact on biomarkers variability and PK of the protocol-required therapies.

**8.2.1.3 Medical History**

The Investigator or designee will collect a complete medical and surgical history that started prior to screening through start of treatment. Medical history will include information on the subject's concurrent medical conditions. Record all findings on the medical history CRF. In addition to the medical history above, the condition under study history must date back to the original diagnosis. The current toxicity grade will be collected for each condition that has not resolved.

**8.2.1.4 Physical Examination**

Physical examination will be performed as per standard of care. Physical examination findings should be recorded on the appropriate CRF (eg, medical history, event).

**8.2.1.5 Physical Measurements**

Height [in centimeters] should be measured without shoes. Weight [in kilograms] should be measured without shoes.

**8.2.1.6 Performance Status**

Subjects will be graded according to the Eastern Cooperative Oncology Group (ECOG) Performance Status. The ECOG criteria for this protocol are further defined in Section 11.9.

**8.2.2 Efficacy Assessments**

Tumor evaluations (by contrast-enhanced computed tomography [CT] or magnetic resonance imaging [MRI]) and tumor markers, if applicable, are to be collected at time points specified in the Schedule of Activities (see Section 1.3). Imaging may also be performed more frequently if clinically necessitated at the discretion of the managing physician.

All radiological imaging will be performed as indicated in the Site Imaging Manual provided by the central imaging core laboratory. In order to reduce radiation exposure for subjects, low dose CT should be utilized whenever possible.

The screening scans must be performed within 28 days prior to enrollment and will be used as baseline. All subsequent scans will be performed in the same manner as at screening, with the same contrast, preferably on the same scanner. Radiological assessments must include MRI/CT of the chest, abdomen and pelvis, as well as assessment of all other known sites of disease as detailed within the Site Imaging Manual.

All subjects must have MRI of the brain performed within 28 days prior to first dose of AMG 994. Subsequently, MRI brain scans may be performed at any time if subject has a history of CNS disease, or if signs or symptoms suggestive of central nervous system metastases are present. All brain scans on protocol are required to be MRI unless MRI is contraindicated, and then CT with contrast is acceptable.

The same imaging modality, MRI field strength and intravenous and oral contrast agents used at screening should also be used for all subsequent assessments. Liver specific MRI contrast agents should not be used. To reduce potential safety concerns, macrocyclic gadolinium contrast agents are recommended per National Health Institute guidelines, or follow local standards if more rigorous.

Eligibility and determination of disease response for clinical management of subjects will be assessed at the clinical sites per Modified RECIST 1.1 (Section 11.11). Scans will be submitted to a central imaging core laboratory for archival and response assessment including Modified RECIST 1.1.

Detailed information regarding submission of images to the central imaging core laboratory is found in the Site Imaging Manual.

Radiographic response (Complete Response, Partial Response) requires confirmation by a repeat, consecutive scan at least 4 weeks after the first documentation of response and may be delayed until the next scheduled scan to avoid unnecessary procedures. Radiographic progression (Progressive Disease) requires confirmation by a repeat, consecutive assessment 4 to 6 weeks after the first detection of radiological progression. Upon discussion with the Sponsor, in the absence of clinical deterioration, subjects may continue to receive AMG 994 and AMG 404 combination treatment after confirmation of radiographic progressive disease as long as they continue to derive clinical benefit, until

clinical disease progression, or intolerance of study treatment, or clinically significant deterioration of health status requiring discontinuation, or the subject withdrawal of consent, whichever occurs first; or, in the absence of the above, up to 12 months if the subject achieves a complete response, and up to 24 months if partial response or stable disease.

If a subject discontinues treatment for reasons other than progression, tumor evaluations should continue according to the Schedule of Activities (see Section 1.3) until progression or start of a new treatment regimen.

### **8.2.3 Safety Assessments**

Planned time points for all safety assessments are listed in the Schedule of Activities (see Section 1.3).

#### **8.2.3.1 Vital Signs**

The following measurements must be performed: systolic/diastolic blood pressure, heart rate, respiratory rate, pulse oximetry, and temperature. Subject must be in a rested and calm state for at least 5 minutes before blood pressure assessments are conducted.

The position selected for a subject should be the same that is used throughout the study and documented on the vital sign CRF. The temperature location selected for a subject should be the same that is used throughout the study and documented on the vital signs CRF. Record all measurements on the vital signs CRF. Oxygen saturation will be measured using a standard pulse oximeter. The temperature location selected for a subject should be the same that is used throughout the study and documented on the vital signs CRF. Record all measurements on the vital signs CRF.

#### **8.2.3.2 Electrocardiograms (ECGs)**

Subject must be in supine position in a rested and calm state for at least 5 minutes before ECG assessment is conducted. If the subject is unable to be in the supine position, the subject should be in most recumbent position as possible. ECGs should be performed in a standardized method, in triplicate, and run consecutively (all 3 ECGs should be completed within a total of 5 minutes from the start of the first to the completion of the third), prior to blood draws or other invasive procedures. Each ECG must include the following measurements: QRS, QT, QTc, RR, and PR intervals.

- 3 baseline ECGs collected  $\geq$  30 minutes apart, with each baseline ECG in triplicate run consecutively (all 3 ECGs should be completed within a total of 5 minutes from the start of the first to the completion of the third) (total 9 ECGs)
- Triplicate ECGs at time points after dosing

Baseline is defined as at screening. The PI or designated sub-investigator will review all ECGs. ECGs will be transferred electronically to an ECG central reader for analysis per Amgen instructions. Once signed, the original ECG tracing will be retained with the subject's source documents. At the request of the sponsor, a copy of the original ECG will be made available to Amgen. Standard ECG machines should be used for all study-related ECG requirements.

#### **8.2.3.3 Vital Status**

Vital status must be obtained for all subjects within the limits of local law. This includes subjects who may have discontinued study visits with or without withdrawing consent and should include interrogation of public databases, if necessary. If deceased, the date and reported cause of death should be obtained.

#### **8.2.4 Adverse Events and Serious Adverse Events**

**The method of recording, evaluating, and assessing causality of adverse events, and serious adverse events and the procedures for completing and transmitting serious adverse event reports are provided in Section 11.4.**

##### **8.2.4.1 Time Period and Frequency for Collecting and Reporting Safety Event Information**

###### **8.2.4.1.1 Adverse Events**

The adverse event grading scale to be used for this study will be the Common Terminology Criteria for Adverse Events (CTCAE) Version 5.0 and is described in Section 11.4.

The investigator is responsible for ensuring that all adverse events observed by the investigator or reported by the subject that occur after first dose of protocol-required therapies through the end of study are reported using the Events CRF.

###### **8.2.4.1.2 Serious Adverse Events**

The investigator is responsible for ensuring that all serious adverse events observed by the investigator or reported by the subject that occur after signing of the informed consent through end of study visit are reported using the Events CRF.

All serious adverse events will be collected, recorded and reported to the sponsor or designee within 24 hours of the investigator's **awareness** of the event, as indicated in Section 11.4. The investigator will submit any updated serious adverse event data to the sponsor within 24 hours of it being available.

Since the criteria for the CTCAE grading scale differs from the regulatory criteria for serious adverse events, **if adverse events correspond to grade 4 CTCAE toxicity grading scale criteria (eg, laboratory abnormality reported as grade 4 without manifestation of life-threatening status), it will be left to the investigator's judgment to also report these abnormalities as serious adverse events. For any adverse event that applies to this situation, comprehensive documentation of the event's severity must be recorded in the subject medical records.**

#### **8.2.4.1.3      Serious Adverse Events After the Protocol-required Reporting Period**

If the investigator becomes aware **of serious adverse events suspected to be related to the investigational product after the protocol-required reporting period (as defined in Section 11.4) is complete, then these serious adverse events will be reported to Amgen within 24 hours following the investigator's awareness of the event.**

**Since a study endpoint is overall survival, the investigator will need to collect/report fatal serious adverse events (regardless of causality) to Amgen within 24 hours following the investigator's awareness of the event.**

**There is no requirement to actively monitor study subjects after the study has ended with regards to study subjects treated by the investigator. However, if the investigator becomes aware of serious adverse events suspected to be related to investigational product, then these serious adverse events will be reported to Amgen within 24 hours following the investigator's awareness of the event.**

Serious adverse events reported outside of the protocol-required reporting period will be captured within the safety database as clinical trial cases and handled accordingly based on relationship to investigational product.

**If further safety related data is needed to fulfill any regulatory reporting requirements for a reportable event, then additional information may need to be collected from the subject's records after the subject ends the study.**

#### **8.2.4.2      Method of Detecting Adverse Events and Serious Adverse Events**

Care will be taken not to introduce bias when detecting adverse events and/or serious adverse events. Open-ended and non-leading verbal questioning of the subject is the preferred method to inquire about adverse event occurrence.

#### **8.2.4.3 Follow-up of Adverse Events and Serious Adverse Events**

After the initial adverse event/serious adverse event report, the investigator is required to proactively follow each subject at subsequent visits/contacts. All adverse events and serious adverse events will be followed until resolution, stabilization, until the event is otherwise explained, or the subject is lost to follow-up (as defined in Section 7.3).

Further information on follow-up procedures is given in Section 11.4.

All new information for previously reported serious adverse events must be sent to Amgen within 24 hours following awareness of the new information. If specifically requested, the investigator may need to provide additional follow-up information, such as discharge summaries, medical records, or extracts from the medical records.

Information provided about the serious adverse event must be consistent with that recorded on the Event CRF.

#### **8.2.4.4 Regulatory Reporting Requirements for Serious Adverse Events**

If subject is permanently withdrawn from protocol-required therapies because of a serious adverse event, this information must be submitted to Amgen.

Prompt notification by the investigator to the sponsor of serious adverse events is essential so that legal obligations and ethical responsibilities towards the safety of subjects and the safety of a study treatment under clinical investigation are met.

The sponsor has a legal responsibility to notify both the local regulatory authority and other regulatory agencies about the safety of a study treatment under clinical investigation. The sponsor will comply with country-specific regulatory requirements relating to safety reporting to the regulatory authority, IRBs/IECs, and investigators.

Individual safety reports must be prepared for suspected unexpected serious adverse reactions according to local regulatory requirements and sponsor policy and forwarded to investigators as necessary.

An investigator who receives an individual safety report describing a serious adverse event or other specific safety information (eg, summary or listing of serious adverse events) from the sponsor will file it along with the Investigator's Brochure and will notify the IRB/IEC, if appropriate according to local requirements.

#### **8.2.4.5 Safety Monitoring Plan**

Subject safety will be routinely monitored as defined in Amgen's safety surveillance and signal management processes.

#### 8.2.4.6      **Pregnancy and Lactation**

Details of all pregnancies and/or lactation in female subjects and female partners of male subjects will be collected after the start of study treatment and until 6 months (**for female subjects**) or 8 months (**for female partners of male subjects**) after the last dose of protocol required therapies.

If a pregnancy is reported, the investigator is to inform Amgen within 24 hours of learning of the pregnancy and/or lactation and is to follow the procedures outlined in Section 11.5. Amgen Global Patient Safety will follow-up with the investigator regarding additional information that may be requested.

Abnormal pregnancy outcomes (eg, spontaneous abortion, fetal death, stillbirth, congenital anomalies, ectopic pregnancy) are considered serious adverse events.

Further details regarding pregnancy and lactation are provided in Section 11.5.

#### 8.2.5      **Clinical Laboratory Assessments**

Refer to Section 11.2 for the list of clinical laboratory tests to be performed and to the Schedule of Activities (Section 1.3) for the timing and frequency.

The investigator is responsible for reviewing laboratory test results and recording any clinically relevant changes occurring during the study in the Event CRF. The investigator must determine whether an abnormal value in an individual study subject represents a clinically significant change from the subject's baseline values. In general, abnormal laboratory findings without clinical significance (based on the investigator's judgment) are not to be recorded as adverse events. However, laboratory value changes that require treatment or adjustment in current therapy are considered adverse events.

Where applicable, clinical sequelae (not the laboratory abnormality) are to be recorded as the adverse event.

All protocol-required laboratory assessments, as defined in Section 11.2, must be conducted in accordance with the laboratory manual and the Schedule of Activities (see Section 1.3).

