### **Dose-Limiting Toxicity**

All events will be graded using the CTCAE version 5.0. The occurrence of any of the following events during the first or second DLT evaluation period will be considered a DLT, excluding events clearly related to disease progression or intercurrent illness:

- Any grade 5 event
- Grade 4 neutropenia or thrombocytopenia of any duration
- Grade 3 thrombocytopenia with clinically significant bleeding or lasting > 7 days
- Febrile neutropenia
- Grade 4 anemia
- Grade 3 or 4 non-hematologic toxicity, with the following exceptions:
  - DLT Exemption: Grade 3 nausea/vomiting or diarrhea < 72 hours in the absence of maximal medical therapy
  - DLT Exemption: Grade 3 fatigue < 1 week

- DLT Exemption: Asymptomatic grade 3 electrolyte abnormalities that last < 72 hours, are not clinically complicated, and resolve spontaneously or respond to conventional medical interventions
- DLT Exemption: Grade 3 amylase or lipase elevations, as per CTCAE version 5.0, grade 4 elevations in amylase and lipase are defined as being associated with signs or symptoms of pancreatitis
- DLT Exemption: Other laboratory parameters of grade 3, not considered clinically relevant, and improved to grade  $\leq 2$  within 72 hours.
- Any grade 3 event requiring hospitalization
- Recurrent grade 2 pneumonitis
- Delay in cycle 2 treatment for  $> 14$  days due to an adverse event in the dose escalation portion of the study due to study drug-related toxicity, except for immune-mediated toxicities as outlined in [Table 11-3](#) where a longer timeframe is specified
- Any other event requiring permanent discontinuation of AMG 994 (for example, as specified in [Table 11-4](#), Infusion-Related Reactions)

[figure not shown]
The cumulative adverse event profile will be taken into consideration when making decisions on dose escalation and on any other dose-level or safety review.

Any subject meeting the criteria for Hy's Law case (ie, severe drug-induced liver injury) will be considered a DLT. A Hy's Law case is defined as: AST or ALT values of  $\geq 3 \times$  ULN AND with serum TBL of  $> 2 \times$  ULN without signs of cholestasis and with no other clear alternative reason to explain the observed liver-related laboratory abnormalities (see Section [6.2.3](#) for hepatotoxicity management and Section [11.7](#) for further explanation of Hy's law case and Management of Hepatic Function).

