exploration the recommended MTD will be the level with the highest probability of the target TPI, but with a less than █ probability of an excessive or unacceptable TPI.

During dose expansion, if the observed rate of responses in a particular tumor type is less than 10% after  $n = 10$  and  $n = 20$  subjects in that tumor type, then enrollment to that tumor type will be terminated due to futility. For purposes of assessing futility, a response is defined as an objective response per modified RECIST 1.1. The guidelines for early termination of enrollment for a tumor type due to futility are as follows:

Number of Treated Subjects in a Tumor Type	Enrollment Stopping Rule
10	0 responders
20	1 or fewer responders
30	Enrollment complete

If the true response rate is 5% then these termination guidelines result in a 78.7% probability of terminating tumor type enrollment at or prior to  $n = 20$  subjects. If the true response rate is 20% then there is an 86.4% probability of continuing enrollment past  $n = 20$  subjects.

During dose expansion, Amgen will conduct evaluations of the ongoing grade 4 or higher treatment-related adverse event rate to assess if the threshold for possible early trial termination has been reached. If this threshold is met, enrollment to dose expansion will be halted pending review of safety data by the DLRT. After receiving the DLRT recommendation, Amgen will choose to take 1 of the following actions.

- Terminate the trial
- Amend the protocol to potentially improve the benefit/risk for subjects (eg, increase safety monitoring, modify dose/schedule, mandate premedication)
- Continue dose expansion without any changes

The stopping rules use a Bayesian approach proposed by Thall, Simon, and Estey (1995) to terminate the study if the posterior probability that the grade 4 or higher treatment-related adverse event rate is greater than 20% is  $> 80\%$ . The stopping boundaries assume a prior distribution of Beta (0.40, 1.60) are presented in [Table 9-1](#) and the operating characteristics with pre-specified batch size of 10 new subjects per batch are presented in [Table 9-2](#). The operating characteristics in [Table 9-2](#) provide the probability of stopping the trial early for given hypothetical true rate of grade 4 or higher treatment-related adverse events, whereas the stopping criteria in [Table 9-1](#) are based

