

• Any abnormal laboratory test results (hematology, clinical chemistry, or urinalysis) or other safety assessments (eg, electrocardiogram, radiological scans, vital signs measurements), including those that worsen from baseline, that are considered clinically significant in the medical and scientific judgment of the investigator (ie, not related to progression of underlying disease).

• Exacerbation of a chronic or intermittent pre-existing condition including either an increase in frequency and/or intensity of the condition.

• New conditions detected or diagnosed after study treatment administration even though it may have been present before the start of the study.

• Signs, symptoms, or the clinical sequelae of a suspected drug-drug interaction.

• Signs, symptoms, or the clinical sequelae of a suspected overdose of either study treatment or a concomitant medication. Overdose per se will not be reported as an adverse event/serious adverse event unless it is an intentional overdose taken with possible suicidal/self-harming intent. Such overdoses are to be reported regardless of sequelae.

• For situations when an adverse event or serious adverse event is due to advanced solid tumors, report all known signs and symptoms. Death due to disease progression in the absence of signs and symptoms should be reported as the primary tumor type (eg, metastatic pancreatic cancer). Note: The term "disease progression" should not be used to describe the adverse event.

• "Lack of efficacy" or "failure of expected pharmacological action" per se will not be reported as an adverse event or serious adverse event. Such instances will be captured in the efficacy assessments. However, the signs, symptoms, and/or clinical sequelae resulting from lack of efficacy will be reported as adverse event or serious adverse event if they fulfill the definition of an adverse event or serious adverse event.

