A best overall response of SD requires an on-study imaging of SD or better no earlier than 7 weeks after cycle 1 day 1; otherwise the best overall response will be not evaluable (NE) unless PD is identified.

Evaluation of overall response details provided in protocol appendix 11.

Change from Baseline

Change from Baseline is the arithmetic difference between post-dose assessments and Baseline value.

Change (absolute) from Baseline = (Post-baseline Value – Baseline Value)

Change (percent) from Baseline = [(Post-baseline Value – Baseline Value)/Baseline Value] x 100

C_{max}

Maximum observed plasma drug concentration.

Dose Limiting Toxicity (DLT)

DLTs are the severe toxicities during the first cycle of cancer therapy. A Dose Limiting Toxicity (DLT) is defined as any AE (meeting the criteria listed in section 6.2.1.5 of protocol) occurring during the first treatment cycle of AMG 994 [REDACTED] where relationship to AMG 404 cannot be ruled out.

The DLT window (DLT-evaluable period) will be the first [REDACTED] of AMG 994 treatment (starting cycle 1, day 1). A subject is evaluable if subject experiences a DLT or completes [REDACTED] of treatment. DLT window will begin from Cycle 2 through study [REDACTED] [REDACTED] for combination of AMG 994 and AMG 404.

Duration of Response (DOR)

The duration of response is defined as time from first evidence of PR or CR to disease progression or death due to any cause. .

DOR will be calculated only for subjects who achieve a confirmed best overall response of PR or better.

DOR (in months) = (Earliest date of disease progression, death, censor - Date of first observation of PR or better + 1)/30.4

Dates of progression and censoring will be determined as described below in table 5.1.

End of Study (End of Trial)

The end of study date is defined as the date when the last subject across all sites is assessed or receives an intervention for evaluation in the study (e.g., last subject last visit), following the final protocol-specified visit (e.g. SFU) or any additional parts in the study (e.g., long-term follow-up, additional antibody testing) whichever is later.

End of Study (Individual Subject)

End of study for each subject is defined as the date the subject last completed a protocol-specified procedure. The date will be recorded on the End of Study CRF page.

End of Study (Primary Completion)

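### In dose expansion, a grade 4 laboratory toxicity deemed not clinically significant need not be recorded as an adverse event, and so may never count toward the Part 2 safety hold rules

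*Protocol*

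**What the plan says.** **Recording.** Protocol 8.2.5 states, as a general rule, that "abnormal laboratory findings without clinical significance (based on the investigator's judgment) are not to be recorded as adverse events". An exception follows at once ("are not to be recorded as adverse events. However, laboratory value changes that require treatment"), and in full it reads: "laboratory value changes that require treatment or adjustment in current therapy are considered adverse events". The adverse event definition in Appendix 4 admits abnormal laboratory results "that are considered clinically significant in the medical and scientific judgment of the investigator". Neither place makes an exception for severity grade.

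**Dose-limiting toxicity.** Protocol 6.2.1 lists "Grade 4 neutropenia or thrombocytopenia of any duration", and also grade 4 anemia, with no significance test. Its general exemption for other laboratory values covers grade 3 only. That exemption needs both a lack of clinical relevance and improvement to grade 2 or below within 72 hours. SAP section 5 words the endpoint differently: "A Dose Limiting Toxicity (DLT) is defined as any AE (meeting the criteria listed in section 6.2.1.5 of protocol". The protocol has no section of that number; the criteria stand in 6.2.1 under the Dose-Limiting Toxicity heading.

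**Expansion monitoring.** Under Protocol 9.4.1.1, "Amgen will conduct evaluations of the ongoing grade 4 or higher treatment-related adverse event rate", and Table 9-1 sets the counts that hold enrollment. The same section suspends accrual after a grade 5 event, or after two occurrences of the same grade 4 adverse event, at least possibly related to either product. Appendix 4 requires a causality assessment for each adverse event.

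**Withholding.** Protocol 6.2.2.2 requires dosing to be withheld for any DLT. Outside the DLT windows, the requirement applies to an adverse event that meets DLT criteria.

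**The concern.** The two sets of rules use different tests. Section 6.2.1 asks what grade the value reached. Section 8.2.5 and Appendix 4 ask whether the investigator thinks it matters. A grade 4 platelet count that causes no symptoms and prompts no action can pass the first test and fail the second.

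Both expansion safety rules take their input from the adverse event data. An unrecorded value has no assigned causality, so it cannot be counted as treatment-related even by someone who sees it in a laboratory listing. Such losses can only lower the count, so any error runs toward a later hold. Protocol 2.1 names thrombocytopenia among the dose-limiting events of systemic CD40 agonists. Section 2.3.1.3 considers it unlikely with AMG 994, and the monitoring rule should be able to test that expectation.

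**Working it through.** **1. Can a value escape? The passages side by side**

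| Setting | Route into the adverse event data for a grade 4 cytopenia deemed not significant |
|---|---|
| Part 1, inside a DLT window | It is a DLT by grade (6.2.1), dosing must be withheld (6.2.2.2), and that is a change in therapy, so 8.2.5 makes it an adverse event. |
| Part 2, or outside a DLT window | 6.2.2.2 protects only an adverse event meeting DLT criteria. The value must already be an adverse event to trigger the step that would make it one. |

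The second row is circular, so a value that leads to no treatment or therapy change can go unrecorded. Section 6.2.1 describes the DLT window as belonging to dose exploration.

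**2. Reproduce Table 9-1**

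Inputs from Protocol 9.4.1.1: prior Beta(0.40, 1.60), limit 20%, posterior threshold 80%. After x events in n subjects, hold if P(p > 0.20 | Beta(0.4 + x, 1.6 + n − x)) > 0.80.

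At n = 20, x = 6 gives 0.826 and x = 5 gives 0.666, so the boundary is 6. The same formula gives 11, 15, 20 and 24 at n = 40, 60, 80 and 100. All five match.

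**3. Reproduce Table 9-2**

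Let f_k(x) be the probability of reaching look k with x events and no earlier hold, and let c_k be the boundary at that look. With batches of 20:

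- f_k(x) = sum over y < c_(k−1) of f_(k−1)(y) × Binomial(x − y; 20, p)
- P(early hold) = sum over k of P(x ≥ c_k at look k)
- Average size = sum of n_k × P(hold at look k) + 120 × P(no hold)

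| True rate | P(early hold) | Average size |
|---|---|---|
| 0.10 | 1.2% | 118.8 |
| 0.15 | 9.6% | 111.5 |
| 0.20 | 37.6% | 90.1 |
| 0.25 | 76.0% | 59.9 |
| 0.30 | 95.7% | 38.0 |

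All match. The text of 9.4.1.1 says batches of 10, which would give 97.2% at a rate of 0.30; the table uses 20.

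**4. Effect of under-recording**

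Recorded rate = true rate × (1 − share missed). The missed share is an assumption, so a range is shown.

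| True rate | Share missed | Recorded rate | P(early hold) | Average size |
|---|---|---|---|---|
| 0.30 | 0% | 0.300 | 95.7% | 38.0 |
| 0.30 | 10% | 0.270 | 86.7% | 49.5 |
| 0.30 | 20% | 0.240 | 69.2% | 65.7 |
| 0.30 | 25% | 0.225 | 57.8% | 74.9 |
| 0.25 | 0% | 0.250 | 76.0% | 59.9 |
| 0.25 | 10% | 0.225 | 57.8% | 74.9 |
| 0.25 | 20% | 0.200 | 37.6% | 90.1 |
| 0.25 | 25% | 0.1875 | 28.5% | 96.9 |

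A single event can matter. Six true events in the first 20 subjects trigger a hold. With one unrecorded, the count is 5, the posterior probability is 0.666, and the next planned look is at 40.

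**The case against.** The strongest reply is that the carve-out in 8.2.5 and the other safeguards already catch these values.

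- **Part 1.** The chain from DLT to withholding to adverse event works inside the window. In sentinel dosing, investigators review laboratory data and confirm DLT status in writing. The model is updated for suspected as well as confirmed DLTs (4.1), and dose level meetings review laboratory results. This stands. A reader might infer that the model is fed too few events and the MTD set too high; the documents do not support that. What remains is a mismatch between the SAP's wording and the grade-based list in 6.2.1.
- **Liver tests.** A reader might infer that these are lost too. Table 11-2 requires withholding from the laboratory value itself where no other cause is identified, for example AST or ALT above 8 × ULN. Table 11-3 places grade 4 above 20 × ULN. Appendix 7 requires concurrent transaminase with bilirubin or INR elevation to be reported as serious, and Hy's Law cases are DLTs outright. This largely stands in both parts.
- **Grade 4 laboratory values as reported events.** Section 8.2.4.1.2 gives a non-life-threatening grade 4 laboratory abnormality as an example and leaves only its seriousness to the investigator. This suggests that such values are expected as adverse events, and the rule in 8.2.5 is only a general one. But 8.2.4.1.2 addresses events already recorded and does not require recording.
- **Other brakes in Part 2.** The two-event suspension may act before Table 9-1, but it counts adverse events too and shares the weakness. The medical monitor may convene a review at any time, but that is discretionary. The SAP 9.6.3 shift tables keep the values for selected parameters and do not feed the boundary.

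**Conclusion.** The gap is real for dose expansion and narrow. It concerns mainly non-hepatic values, above all grade 4 neutropenia and thrombocytopenia, that are deemed not significant and lead to no treatment or therapy change. These values remain in the laboratory data; the adverse event counts that drive the hold rules can lose them. In Part 1 the point is mainly one of wording.

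The size cannot be derived from the documents. The figures in the working assume that a fixed share of related grade 4 or higher events is missed at random across subjects, with looks every 20 subjects. At a true rate of 30%, a 10% loss costs 9 percentage points of early-hold probability (95.7 − 86.7) and a 25% loss costs 37.9 (95.7 − 57.8).

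A reader might set Table 9-2's 95.7% against its 37.6% and take that as the effect. That requires one third of all related grade 4 or higher events to go unrecorded (0.30 × 2/3 = 0.20), and nothing in the documents supports that share. Nor do they settle that every grade 4 laboratory value should count; the supported change is limited to values meeting a 6.2.1 criterion.

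**What to change.** 1. **Protocol 8.2.5 and Appendix 4.** Reconcile these with 6.2.1 by adding one sentence: any laboratory value that meets a 6.2.1 DLT criterion, in either study part and inside or outside a DLT window, is recorded on the Events CRF with grade and causality, whatever its deemed clinical significance.
2. **SAP section 5.** Align the DLT definition with the list in 6.2.1 and correct the section reference.
3. **Reconciliation.** Before each dose level review meeting and each boundary look, compare graded laboratory data with the Events CRF. Query the investigator about any unrecorded qualifying value. The query is needed because a programmed listing carries no causality and cannot correct a count of related events by itself.

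The cost is one protocol sentence, one SAP edit, one programmed listing from data already collected, and a few more recorded events and queries. The change affects recording only; it alters no dose or treatment rule.
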